## 8.2.5.6 Guidelines for management of macular degeneration

In cases of suspected macular degeneration or acute vision loss, participants will be referred for an ophthalmological consultation.

#### 8.3 Serious Adverse Events

An AE or adverse reaction is considered serious if, in the view of either the Investigator or Sponsor, it results in any of the following outcomes:

- Death;
- A life-threatening AE;

Note: An AE or adverse reaction is considered "life-threatening" if, in view of either the Investigator or Sponsor, its occurrence places the participant at immediate risk of death. It does not include an event that, had it occurred in a more severe form, might have caused death.

• Requires hospitalization or prolongation of existing hospitalizations;

Note: Any hospital admission with at least 1 overnight stay will be considered an inpatient hospitalization. An emergency room or urgent care visit without hospital admission will not be recorded as an SAE under this criterion, nor will hospitalization for a procedure scheduled or planned before signing of informed consent, or elective treatment of a pre-existing condition that did not worsen from Baseline. However, unexpected complications and/or prolongation of hospitalization that occur during elective surgery should be recorded as AEs and assessed for seriousness. Admission to the hospital for social or situational reasons (ie, no place to stay, live too far away to come for hospital visits, respite care) will not be considered inpatient hospitalizations.

- A persistent or significant disability/incapacity or substantial disruption of the ability to conduct normal life functions:
- A congenital anomaly/birth defect; or
- An important medical event.

Note: Important medical events that do not meet any of the above criteria may be considered an SAE when, based upon appropriate medical judgment, they may jeopardize the participant and may require medical or surgical intervention to prevent 1 of the outcomes listed above. Examples of such medical events include allergic bronchospasm requiring intensive treatment in an emergency room or at home, blood dyscrasias or convulsions that do not result in inpatient hospitalizations, or the development of drug dependency.

SAEs that meet the definition of CV outcome events should also be captured in the CV events eCRF.

The plan for exemption from expedited SAE reporting for disease-related events will be described in the Statistical Analysis Plan (SAP), Data Management Plan, and CEC Charter documents.

## 8.4 SAE Reporting – Procedures for Investigators

Initial reports
All SAEs occurring from the time of informed consent until the end of study participation (up to 35 days post last dose) will be reported, regardless of the Investigator's determination as to relatedness, to within 24 hours of the knowledge of the occurrence. After the 30-day reporting window, any SAE that the Investigator considers related to study drug must be reported to or the Sponsor/designee ( ).
To report the SAE, complete the SAE form electronically in the EDC system for the study. If the event meets serious criteria and it is not possible to access the EDC system, send an email to at a criteria are or call the SAE reporting line (telephone number listed in Section 8.7), and fax/email the completed back-up paper SAE form to contact information listed in Section 8.7) within 24 hours of awareness. When the EDC system becomes available, the SAE information must be entered within 24 hours of the system becoming available.
Follow-up reports
The Investigator must continue to follow the participant until the SAE has subsided or until the condition becomes chronic in nature, stabilizes (in the case of persistent impairment), or the participant dies.
Within 24 hours of receipt of follow-up information, the Investigator must update the SAE form electronically in the EDC system for the study and submit any supporting documentation (eg, participant discharge summary or autopsy reports) to via fax or email. If it is not possible to access the EDC system, refer to the procedures outlined above for initial reporting of SAEs.
8.5 Pregnancy Reporting
If a participant becomes pregnant during the study, the Investigator is to stop dosing with the study drug immediately and permanently. However, the participant should be encouraged to remain in the study and to follow-up for study visits. See Section 4.3 for more details regarding withdrawal criteria and discontinuation of study drug.
A pregnancy is not considered to be an AE or SAE; however, it must be reported to within 24 hours of knowledge of the event. will then provide the Investigator/site the Exposure In Utero (EIU) form (Part 1) for completion. The Investigator/site must complete the EIU form (Part 1) and fax/email it back to
If the female partner of a male participant becomes pregnant while the participant is receiving study drug, the Investigator should notify as described above.
The pregnancy should be followed until the outcome of the pregnancy is known, whenever possible. Once the outcome of the pregnancy is known, the EIU form (Part 2) should be completed and faxed/emailed to

for reporting an SAE.

for immediate classification as an SAE (ie, postpartum complication, spontaneous abortion, stillbirth, neonatal death, or congenital anomaly), the Investigator should follow the procedures

## 8.6 Expedited Reporting

The Sponsor/designee (SUSARs) will report all relevant information about Suspected Unexpected Serious Adverse Reactions (SUSARs) that are fatal or life-threatening to the FDA, applicable Competent Authorities in all Member States (including all Institutional Review Boards [IRBs]/Independent Ethics Committees [IECs]), and to the Central Ethics Committees no later than 7 calendar days (CDs) after knowledge by the Sponsor/designee of such a case. Relevant follow-up information will subsequently be communicated within an additional 8 CDs.

All other SUSARs will be reported to the FDA, applicable Competent Authorities in all Member States (including all IRBs/IECs), and to the Central Ethics Committees within a maximum of 15 CDs of first knowledge by the Sponsor/designee.

The Sponsor/designee will also report any additional expedited safety reports required in accordance with the timelines outlined in country-specific legislation.

The Sponsor/designee will also inform all Investigators as required per local regulation.

The requirements above refer to the requirements relating to study drug.

## 8.6.1 Project Specific Exemption From SAE Immediate Reporting to Health Authorities and IRBs

The guidance document of the Committee for Medicinal Products for Human Use (CHMP), "Detailed guidance on the collection, verification and presentation of adverse event/reaction reports arising from clinical trials on medicinal products for human use," states that for trials in high morbidity and/or high mortality disease, where efficacy endpoints could also be adverse reactions reported as SUSARs, these serious events could be treated as disease-related events and not be subject to systematic unblinding and expedited reporting.

Moreover, the FDA guidance documents titled "Guidance for clinical investigators, sponsors, and IRBs. Adverse event reporting to IRBs – improving human subject protection" and "Guidances for industry and investigators on safety reporting requirements for investigational new drug applications and bioavailability/bioequivalence studies" state that only AEs which are unexpected, serious, and would have implications for the conduct of the study should be reported in an expedited manner. 

Aggregate unblinded analysis by the independent DSMB will be conducted in order to identify safety concerns, such as potential imbalances in event rates between the drug treatment and control groups. Should the DSMB identify any potential safety concerns, they will be able to recommend reporting of these findings to the Health Authorities (HA), Investigators, Ethics Committees, and IRBs. Additionally, the DSMB will have the freedom to determine, based on their ongoing review of the safety data, if any of the exempted AEs should be changed to become subject to expedited reporting from that point on. A safety report will be submitted if an aggregate analysis indicates the anticipated SAEs are occurring more frequently in the treatment group compared to the placebo group.

## 8.7 Special Situation Reports

Special situation reports include reports of overdose, misuse, abuse, medication error, and reports of adverse reactions associated with product complaints.

- Overdose: Refers to the administration of a quantity of a medicinal product given per
  administration or cumulatively (accidentally or intentionally), which is above the maximum
  recommended dose according to the protocol. Clinical judgment should always be applied. In
  cases of a discrepancy in the drug accountability, overdose will be established only when it is
  clear that the participant has taken additional dose(s), or the Investigator has reason to suspect
  that the participant has taken additional dose(s).
- Misuse: Refers to situations where the medicinal product is intentionally and inappropriately
  used in a way that is not in accordance with the protocol instructions or local prescribing
  information and may be accompanied by harmful physical and/or psychological effects.
- Abuse: Is defined as persistent or sporadic, intentional excessive use of a medicinal product, which is accompanied by harmful physical or psychological effects.
- Medication error: Is any unintentional error in the prescribing, dispensing, or administration
  of a medicinal product by a healthcare professional, participant, or consumer, respectively. The
  administration or consumption of the unassigned treatment and administration of an expired
  product are always reportable as medication errors; cases of participants missing doses of
  investigational product are not considered reportable as medication errors.
- Product complaint: Is defined as any written, electronic, or oral communication that alleges
  deficiencies related to the identity, quality, durability, reliability, safety, effectiveness, or
  performance of a drug or device after it is released for distribution. A special situations form
  will only be completed if a complaint is associated with an adverse drug reaction.

All special situation events as described above must be reported on the special situation report form and faxed/emailed to (contact information listed below) within 24 hours of knowledge of the event. In addition, all special situation events must be entered into the EDC system within 24 hours of knowledge of the event. All AEs associated with these special situation reports should be reported as AEs or SAEs as well as recorded on the AE eCRF and/or the SAE report form. Details of the symptoms and signs, clinical management, and outcome should be provided, when available.

Safety Contact Information:			
T-1		_	
Telephone: Fax:			
Email:			
'			
Telephone:			
Fax:			
Email:			

## 8.8 Clinical Laboratory Evaluations

Clinical laboratory evaluations (including a full serum chemistry panel, hematology, coagulation, and urine dipstick analysis) will be collected at visits specified in the Schedule of Procedures (Appendix A). A limited serum chemistry panel will also be collected per the Schedule of Procedures (Appendix A). All safety laboratory samples should be collected while the participant is fasting (a minimum of 8 hours) and prior to the next dose of study drug (at applicable visits). Assessment of laboratory eligibility criteria will be based on central laboratory values obtained within timeframes defined in the inclusion and exclusion criteria.

Urine dipstick analysis will be performed locally from a sample of mid-stream urine. In case of abnormal results, microscopy and other assessments will be performed at the local laboratory and the abnormality recorded as an AE.

Please see Appendix B for a complete list of laboratory analytes.

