#### 8.2 Adverse Events

An AE is defined as any untoward medical occurrence in a clinical investigation participant administered a pharmaceutical product, which does not necessarily have a causal relationship with this treatment. An AE can therefore be any unfavorable and/or unintended sign (including an abnormal laboratory finding), symptom, or disease temporally associated with the use of an investigational medicinal product, whether or not related to the investigational medicinal product. All AEs, including observed or volunteered problems, complaints, or symptoms, are to be recorded on the appropriate eCRF.

AEs, which include clinical laboratory test variables, will be monitored and documented from the time of signing of informed consent at Screening (Visit 1) until the EOS Visit (35 days after the EOT Visit). Participants should be instructed to report any AE that they experience to the Investigator, whether or not they think the event is due to study treatment. Beginning at the time of signing of informed consent, Investigators should make an assessment for AEs at each visit and record the event on the appropriate AE eCRF.

Wherever possible, a specific disease or syndrome rather than individual associated signs and symptoms should be identified by the Investigator and recorded on the eCRF. However, if an observed or reported sign or symptom is not considered a component of a specific disease or syndrome by the Investigator, it should be recorded as a separate AE on the AE eCRF. Additionally, the condition that led to a medical or surgical procedure (eg, surgery, endoscopy, tooth extraction, or transfusion) should be recorded as an AE, not the procedure itself.

Any medical condition already present at Screening (Visit 1) should be recorded as medical history and not be reported as an AE unless the medical condition or signs or symptoms present at Baseline changes in severity, frequency, or seriousness at any time during the study. In this case, it should be reported as an AE.

Clinically significant abnormal laboratory or other examination (eg, ECG) findings that are detected during the study or are present at Screening (Visit 1) and significantly worsen during the

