#### 8.8.4 Managing Abnormal and Critical Laboratory Values

Any laboratory test result abnormality that fulfills the criteria for an SAE will be reported as such on the appropriate AE and SAE eCRF. Any treatment-emergent abnormal laboratory result that is clinically significant, ie, meets 1 or more of the following criteria, will be recorded as a single diagnosis on the AE eCRF:

- Is accompanied by clinical symptoms;
- Leads to a change in study drug (eg, study drug interruption or permanent discontinuation); and/or
- Requires a change in concomitant therapy or a medical intervention (eg, the addition of, interruption of, or discontinuation of, or any other change in a concomitant medication, therapy, or treatment).

These criteria apply to any protocol and non-protocol-specified safety and/or efficacy laboratory results from tests performed after the first dose of study drug that meet clinical significance criteria. These criteria do not apply to any abnormal laboratory test results which fall outside the laboratory reference range, but which do not meet clinical significance criteria (these will be analyzed and reported as laboratory abnormalities) or those which are a result of an AE or an endpoint which has already been reported.

The Investigator is responsible for reviewing laboratory test results and determining whether an abnormal value in an individual participant represents a clinically significant change from the participant's Baseline values. In general, laboratory abnormalities without clinical significance should not be recorded as AEs. Where applicable, the clinical sequelae, not the laboratory abnormality, should be recorded as the AE.

Critical laboratory values are values that may warrant medical intervention to avoid possible harm to a participant. Critical laboratory values will be defined in the Laboratory Manual for the study, and the Medical Monitor and Investigator will be notified of the occurrence of a critical laboratory value (critical high or critical low) by a special annotation (flag) in the laboratory reports provided to the sites.

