## **APPENDIX A: SCHEDULE OF PROCEDURES**

	Screening			Treatn	nent Period			EOS 
Visit	V1	V2	V3	V4	V5	V6	V7/EOT/ET 	V8
								35 days after
Study Day		1	30	84	180	270	365	last dose
Window (±days)			±3	±7	±7	±7	±7	±7
Informed consent 	X							
Assessment of eligibility	X 	$X^4$						
Demographics and medical history	X							
Pregnancy test, FSH 	X	X			X		X	
TSH	X							
Randomization		X						
Study drug administration		X	X	X	X	X	X	
Physical examination 	X						X	
Weight, height, and BMI	X 						X	
Vital signs 	X	X	X	X	X	X	X	X
24-hr ABPM 	$X^{10}$					X 		
12-lead ECG 		X					X	
Lipid profile/biomarkers (fasting) 	X	X	X	X	X	X	X	
Serum archive sample for future								
assessment of biomarkers related to								
dyslipidemia and/or CV risk (fasting) 		X					X	
UACR, UPCR (fasting) 		X					X	
Aldosterone, hsCRP (fasting) 	$X^{16}$	X					X	
Lp(a), ApoA1 (fasting) 	X	X		X				
Insulin for HOMA-IR (fasting) 	X	X		X	X	X	X	
Full serum chemistry (fasting) 		X			X		X	
Limited serum chemistry (fasting) 	X		X	X		X		
Urine dipstick analysis 	X	X					X	
Hematology and coagulation (fasting) 	X	X			X		X	
PK sample (central) 		X			X		X	
Prior/concomitant medications	X	X	X	X	X	X	X	X
Study drug dispensation		X	X	X	X	X		

Footnotes are at the end of the table.

	Screening		Treatment Period			EOS 		
Visit	V1	V2	V3	V4	V5	V6	V7/EOT/ET 	V8
St. I. D	20.4 1		20	0.4	100	250	265	35 days after
Study Day	-28 to -1	1	30	84	180	270	365	last dose
Window (±days)			±3	±7	±7	±7	±7	±7
Study drug return/compliance calculations			X	X	X	X	X	
CV events assessment 	X	X	X	X	X	X	X	X
AEs assessment	X	X	X	X	X	X	X	X

- 1. The onsite EOS Visit will include an assessment of vital signs, concomitant medications, CV events, and AEs will be completed and documented in the participant's record.

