- 11. It should be ensured that a repeat assessment (if necessary) is completed within the respective visit window and that the assessment is not done concurrently with other study procedures.
- 12. A single 12-lead ECG will be performed in the supine position after 10 minutes of rest.
- 13. Participants must fast for a minimum of 8 hours prior to samples being collected.
- 14. Samples should be collected prior to study drug administration.
- 15. Serum archive sample is not collected in China.
- 16. Only hsCRP will be assessed at Screening (Visit 1).
- 17. Urine dipstick analysis will be performed locally from a sample of mid-stream urine. In case of abnormal results, microscopy and other assessments will be performed at the local laboratory and the abnormality recorded as an AE.
- 18. A PK sample will be collected prior to study drug administration for trough measurement of obicetrapib in plasma. At Visits 2, 5, and 7, participants should take study drug after a trough PK sample has been drawn.
- 19. CV events include CV death, non-fatal myocardial infarction, non-fatal stroke, non-elective coronary revascularization, hospitalization for unstable angina and/or chest pain, hospitalization for heart failure, and transient ischemic attack.

ABPM = ambulatory blood pressure monitoring; AE = adverse event; ApoA1 = apolipoprotein A1; BMI = body mass index; CV = cardiovascular; ECG = electrocardiogram; EOS = End of Study; EOT = End of Treatment; ET = Early Termination; FSH = follicle-stimulating hormone; HOMA-IR = homeostatic model assessment of insulin resistance;

hsCRP = high sensitivity C-reactive protein; ICF = informed consent form; Lp(a) = lipoprotein (a); PK = pharmacokinetic(s); TSH = thyroid-stimulating hormone; UACR = urine albumin-creatinine ratio; UPCR = urine protein-creatinine ratio; V = Visit.

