### **Urine Dipstick Analysis**

Bilirubin Blood Glucose Ketones

Leukocyte esterase Microscopy [1]

Nitrite pH

Protein Urobilinogen

1. Urine dipstick analysis will be performed locally from a sample of mid-stream urine. In case of abnormal results, microscopy and other assessments will be performed at the local laboratory and the abnormality recorded as an adverse event.

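### Any abnormal urine dipstick is to be recorded as an AE, which conflicts with the protocol's own rules on Screening findings and clinical significance and can put non-events into the TEAE tables

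*Protocol*

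**What the plan says.** Protocol 8.8 sets the rule for local urine dipsticks: "In case of abnormal results, microscopy and other assessments will be performed at the local laboratory and the abnormality recorded as an AE". Appendix A footnote 17 repeats it ("microscopy and other assessments will be performed at the local laboratory and the abnormality recorded as an AE"), as does the note to the dipstick panel in Appendix B ("microscopy and other assessments will be performed at the local laboratory and the abnormality recorded as an adverse event"). SAP Table 1 footnote 17 carries it as well. The panel in Appendix B includes bilirubin, blood, glucose, ketones, leukocyte esterase, nitrite, protein and urobilinogen. Appendix A schedules the dipstick at Visit 1 (Screening), Visit 2 (Day 1) and Visit 7/EOT/ET.

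Three other statements bear on the same results:

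- Protocol 8.2, on pre-existing conditions: "Any medical condition already present at Screening (Visit 1) should be recorded as medical history and not be reported as an AE". The sentence goes on to except conditions that change in severity, frequency or seriousness.
- Protocol 8.2, on laboratory findings: they are AEs when clinically significant and, if already present at Screening, when they significantly worsen. The Investigator judges significance. The triggers listed are a required intervention, action taken with study drug, or Investigator judgment.
- Protocol 8.8.4: "In general, laboratory abnormalities without clinical significance should not be recorded as AEs". Results outside the reference range that do not meet its significance criteria are to be handled as laboratory abnormalities.

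AEs "will be monitored and documented from the time of signing of informed consent at Screening (Visit 1) until the EOS Visit", so a Screening dipstick falls inside the collection window. SAP 3.5.1 tabulates and lists treatment-emergent AEs, including a table of non-serious TEAEs above 2% by preferred term.

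**The concern.** A site with a stable, clinically unimportant dipstick finding has two instructions. The dipstick sentence says to record an AE. Sections 8.2 and 8.8.4 point to medical history or to a laboratory abnormality. A participant with type 2 diabetes, one of the listed risk enhancers, and long-standing glycosuria is a simple example.

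Two things are at stake. With about 180 planned sites, AE counts may depend partly on which instruction a site follows. And where the dipstick sentence is followed, findings that the rest of the protocol would not call AEs enter the safety tables. Each then needs a severity grade and a causality call, so it can also appear in the severity tables and, if judged related, in the drug-related tables.

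**Working it through.** The documents state no figure on this point, so there is nothing to reproduce. The main check is textual, visit by visit.

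| Visit | Dipstick sentence | Other protocol rule | Reaches the SAP TEAE tables? |
|---|---|---|---|
| V1, Screening | AE | 8.2: medical history unless it changes; a laboratory finding present at Screening is an AE if clinically significant and significantly worsened | Should not: before treatment |
| V2, Day 1 | AE | 8.2: Investigator judges significance | Unclear: see below |
| V7/EOT/ET | AE | 8.2, and 8.8.4: non-significant results are in general not AEs | Yes: after first dose |

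The 8.8.4 criteria apply to tests after the first dose, so that section bears on V7. Section 8.2 bears on all three visits.

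**Day 1.** Protocol 8.8 places safety laboratory samples "prior to the next dose of study drug (at applicable visits"), so the V2 dipstick should be pre-dose. The schedule row itself ("Urine dipstick analysis 17") carries only footnote 17 and not the pre-dose footnote, so this timing rests on 8.8. SAP 3.1.1 makes the day of first dose Day 1. SAP 3.1.8 and 3.5.1 use treatment-emergent status, but the SAP text available does not define it. A V2 finding dated Day 1 would count as a TEAE if status were assigned by date alone.

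**Scale, for illustration only.** Inputs: N = 2400, randomized 2:1, so about 1600 and 800 (documents); no dropout (assumption); abnormal rate p per dipstick, 2% to 30% (assumption). Abnormal dipsticks per visit = 2400 × p.

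| p | V7 only | V1 + V2 | All three visits |
|---|---|---|---|
| 2% | 48 | 96 | 144 |
| 5% | 120 | 240 | 360 |
| 10% | 240 | 480 | 720 |
| 20% | 480 | 960 | 1440 |
| 30% | 720 | 1440 | 2160 |

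Only the V7 column is clearly post-dose, one dipstick visit per participant. Two thirds of the total is V1 plus V2.

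**The 2% table.** A preferred term enters if it exceeds 2% in either arm: at least 17 of 800 (0.02 × 800 = 16) or at least 33 of 1600 (0.02 × 1600 = 32). Here the assumed rate is for one dipstick term, not for any abnormality. The exact binomial tail is 0.434 (placebo) and 0.453 (obicetrapib) at a true rate of 2%, and 1.0 to three decimals in each arm at 5%.

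**Dilution.** If V7 abnormalities occur at rate p in both arms, independently of other AEs, the observed risk is 1 − (1 − b)(1 − p) for a true risk b, and the risk difference shrinks by the factor (1 − p). An assumed difference of 5.0 points becomes 5.0 × 0.95 = 4.75 at p = 5% and 5.0 × 0.70 = 3.5 at p = 30%.

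**The case against.** The strongest reply is that a specific dipstick rule can stand beside general ones. Section 8.8.4 says in general, and the trigger list in 8.2 says when a finding should be an AE without saying that nothing else may be one. Neither section limits recording to clinically significant results in so many words, and under 8.2 new, worsened or Investigator-judged glycosuria at Day 365 could properly be an AE. This stands as far as it goes: the conflict is not absolute. But no exception is declared, cross-referenced or explained in any of the four places, and for a stable Screening finding the medical-history rule points the other way.

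A reader might infer that the AE tables will be flooded, chiefly by Screening findings. The documents do not support that. The SAP AE tables cover TEAEs only, one dipstick per participant is clearly post-dose, and no abnormality rate is given. Nor do they show that glycosuria is typical here: diabetes and SGLT2 use are baseline yes/no variables with no prevalence stated. Nor do they say that a persisting finding becomes a new AE at each visit.

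The consequences are also bounded. SAP 3.5 applies no inference to safety endpoints, so no AE test loses power. Tabulation by preferred term leaves dipstick terms visible. Renal safety is also followed through eGFR and creatinine criteria and through shift tables of urine albumin and protein ratios. Under blinding, the noise should fall on both arms.

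**Conclusion.** The inconsistency holds: four unqualified sentences conflict with 8.2 on Screening findings and Investigator judgment, and with 8.8.4 on non-significant results. If sites follow the dipstick sentence, non-significant V7/EOT/ET findings become TEAEs in both arms and may reach the table of terms above 2%. The effect is avoidable noise and possible differences between sites in recording, not a demonstrated distortion. Its size cannot be stated; every count, probability and dilution figure above rests on assumed rates. Screening findings should not reach the SAP tables. Protocol 9.2.2, however, does not limit its AE summaries to treatment-emergent events, and pre-dose Day 1 findings remain unclassified until the SAP defines the term. No endpoint, estimand, alpha or power figure is affected.

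**What to change.** 1. In Protocol 8.8, Appendix A footnote 17, Appendix B and SAP Table 1 footnote 17, replace the closing clause with: *and the abnormality recorded as an AE if it meets the laboratory AE criteria in Sections 8.2 and 8.8.4; findings present at Screening are recorded as medical history unless they worsen as described in Section 8.2*. The two lists differ: 8.8.4 names accompanying symptoms, while 8.2 names Investigator judgment. State whether meeting either is enough.
2. Define treatment-emergent in the SAP, and state that pre-dose Day 1 findings are not treatment-emergent. Date alone cannot separate them, so tie the rule to the Visit 2 sample.
3. For data already collected, flag before unblinding the AEs whose only basis is a dipstick result, and show the TEAE overview with and without them. Nothing is deleted.

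The cost is one clause in four places, one SAP definition, a blinded flagging step and one extra table. No participant procedure changes.
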